Since participation in this study was voluntary and conducted with volunteers, it was reviewed by the Clinical Research Ethics Committee of Afyonkarahisar Health Sciences University. The study was unanimously deemed to comply with medical ethical standards (Date: 07.04.2023, Protocol Code: 2023/4). All volunteers signed an informed consent form approved by the ethics committee before participating in the study.

Volunteer Selection

This study included 100 volunteer patients who applied to the Department of Prosthetic Dentistry at Afyonkarahisar Health Sciences University Faculty of Dentistry for prosthetic treatment and received a single-unit implant-supported crown. Patients were selected from archives and evaluated during their 12-month follow-up appointments through clinical and radiographic examinations. To determine the number of volunteers needed for the study, a sample size calculation was performed using *GPower software* (*GPower* Ver. 3.0.10, Franz Faul, University of Kiel, Germany). With a significance level of $\alpha=0.05$ (95% confidence interval), an effect size (d) of 0.5, and power ($1-\beta$) = 0.80, at least 80 patients were required. To account for potential dropout and data loss during follow-up, an additional 25% (20) patients were added, resulting in 100 patients at the start of the study.

Systemic and dental anamneses of the volunteers were thoroughly evaluated, and inclusion and exclusion criteria were established. Patients meeting the inclusion criteria were provided detailed information about the study plan before the start. Those who agreed to participate signed the

Inclusion Criteria

1. Patients who had received single-unit dental implant treatment and had 12 months elapsed since prosthetic loading.
2. Patients aged 18 and older, regardless of gender.
3. Patients with no systemic health issues.
4. Non-smokers.
5. Patients for whom radiographic bone loss, mobility, and prosthetic complications data were recorded and evaluated.
6. Patients who signed the informed consent form voluntarily after being fully informed about the study's purpose, duration, and requirements.

Exclusion Criteria

1. Patients diagnosed with osteoporosis and/or undergoing bisphosphonate treatment during or after treatment.
2. Patients with uncontrolled systemic diseases (e.g., diabetes mellitus, heart diseases, liver diseases).
3. Patients with a history of head or neck radiotherapy.
4. Patients on chronic medication (e.g., steroids, antidepressants).

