5. Smokers.
6. Patients without radiographs immediately after prosthetic loading.
7. Patients with psychiatric problems.
8. Patients with missing data on radiographic bone loss, mobility, prosthetic complications, or implant dimensions.
9. Patients with short implant designs.
10. Patients who lost implants before the 12-month follow-up.

Data Collection

The evaluations conducted during the patients' 12-month follow-up appointments were recorded and analyzed. The parameters assessed during these appointments include:

A. Demographic Data

1. Age of the patient.
2. Gender of the patient (Male/Female).
3. Education level (Primary School, Secondary School, High School, Undergraduate, Graduate).

B. Clinical Parameters

1. Tooth brushing habits (None, Once daily, Twice daily, More than twice daily).
2. Presence of functional pain (Yes/No).
3. Mobility (Yes/No).
4. Presence of exudate (Yes/No).
5. Attached gingiva (≥ 3 mm) (Yes/No).
6. Reason for tooth extraction (Endodontic, Periodontal, Other).
7. Immediate implant placement after extraction (Yes/No).
8. Implant diameter (Narrow < 3.75 mm, Standard ≥ 3.75 mm and < 5 mm, Wide ≥ 5 mm).
9. Implant length (Short implants excluded; Standard ≥ 10 mm).
10. Implant type by tissue relationship (Bone Level, Tissue Level).
11. Anatomical location of the implant (Maxillary Anterior/Posterior, Mandibular Anterior/Posterior).
12. Type of abutment (Standard, Screw-Retained, Ti-Base).
13. Status of the opposing arch (Natural Tooth, Tooth-Supported Fixed Prosthesis, Implant-Supported Fixed Prosthesis, Implant-Supported Removable Prosthesis, Tooth-Supported Removable Partial Prosthesis/Full Denture).
14. Occlusal table dimensions (Normal/Reduced by 30-40%).
15. Superstructure material (Metal-Ceramic, Monolithic Zirconia, Monolithic Glass Ceramic).
16. Presence and history of screw loosening (Yes/No).
17. Presence and history of cementation loss (Yes/No).
18. Framework-ceramic separation (Chipping) (Yes/No).

Data Evaluation

Evaluation of Implant Success and Survival

The success and survival of the implants were evaluated based on the 2007 consensus criteria established by the International Congress of Oral Implantologists (ICOI). The data were categorized

into four groups: Healthy-Successful, Sufficient Survival, Compromised Survival, and Unhealthy-Failed.

Evaluation of Radiographic Bone Loss

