Digital radiographs (periapical and panoramic films) taken at the end of prosthetic treatment and during the 12-month follow-up were analyzed using Planmeca Romexis® software (Planmeca, Helsinki, Finland). Marginal bone loss was measured using ImageJ software (ImageJ 1.54g, NIH, USA). Measurements were calibrated based on the actual implant length. The mesial and distal marginal bone loss was calculated separately by subtracting the values obtained immediately after prosthetic loading from those at the 12-month follow-up.

Statistical Analysis

The collected data were analyzed using SPSS Statistics V.26 (IBM SPSS Statistics, USA). The normality of parameters was assessed using the Kolmogorov-Smirnov and Shapiro-Wilk tests. Descriptive statistical methods (mean, standard deviation, median, frequency) were employed. Quantitative data and intergroup comparisons were evaluated using the Kruskal-Wallis test, with Dunn's test for post hoc analysis. The Mann-Whitney U test was used for pairwise comparisons, and the Fisher-Freeman-Halton Exact Chi-Square test was employed for qualitative data comparisons. A significance level of $p<0.05$ was considered statistically significant.

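### No rule requires a patient's two radiographs to be the same film type, so any mixed periapical–panoramic pair would carry a film-type difference into marginal bone loss

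*Combined protocol and SAP*

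**What the plan says.** Under Evaluation of Radiographic Bone Loss: "Digital radiographs (periapical and panoramic films) taken at the end of prosthetic treatment and during the 12-month follow-up were analyzed". The only correction described is "Measurements were calibrated based on the actual implant length". Mesial and distal bone loss are then "calculated separately by subtracting the values obtained immediately after prosthetic loading from those at the 12-month follow-up".

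On where the films come from, Volunteer Selection says "Patients were selected from archives and evaluated during their 12-month follow-up appointments through clinical and radiographic examinations". The only eligibility rule on the baseline film is exclusion 6, which removes "Patients without radiographs immediately after prosthetic loading"; it does not specify the type of film.

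Under Statistical Analysis, "Quantitative data and intergroup comparisons were evaluated using the Kruskal-Wallis test, with Dunn's test for post hoc analysis", with Mann-Whitney for pairwise comparisons, and "A significance level of $p<0.05$ was considered statistically significant". No film-type factor, stratum or sensitivity analysis is mentioned. Among the recorded parameters is "Anatomical location of the implant (Maxillary Anterior/Posterior, Mandibular Anterior/Posterior" (Clinical Parameters, item 11).

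Outcome Measures names implant survival and prosthetic complication rate as primary. Bone resorption is in the study title but is not listed there as an outcome measure.

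**The concern.** A change score is safe from a constant measurement offset only if the offset is the same at both times. Two films of the same type share whatever systematic error that type has in locating the crest, and subtraction removes it. A periapical and a panoramic film need not share it. One scale factor taken from implant length corrects magnification along the implant. It does not equalise projection angle, sharpness or overlap at the crest, which is where the reading is made.

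The plan accepts both types at both times and states no pairing rule. The baseline film of an archive-selected patient may be whatever was taken at the time. As written, the method allows mixed pairs and describes no step that would reveal them. At stake is the bone-loss endpoint: a comparison between groups could show a difference that comes from imaging, or could lose precision.

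**Working it through.** The plan gives no figure on this point to reproduce: no bone-loss SD, no film-type difference and no count of mixed pairs. Everything numerical below is an illustration with assumed inputs.

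**How the shift enters.** Let each reading be the true crest level plus an offset for its film type, and let b be the difference between the two offsets.
- Same-type pair: measured change = true change + 0.
- Mixed pair, one order: true change + b.
- Mixed pair, reverse order: true change − b.

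Let m be a group's share of mixed pairs and q the fraction of those in the +b order. With SD σ of true change:
- mean shift = (2q − 1)·m·b
- variance = σ² + m·b² − [(2q − 1)·m·b]²

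The spurious difference between two groups is (2q − 1)·b·(m₂ − m₁). It is zero if q = 0.5 or if the shares are equal.

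**Assumed inputs.** σ = 0.4 mm; b = 0.3 mm; 50 patients per group (half of the plan's 100 each); m₁ = 10%; m₂ = 30%, 50% or 70%; no true difference; two-sided 0.05 (the plan gives 0.05 but not the sidedness). Rejection probability = Φ(z − 1.96) + Φ(−z − 1.96), where z = difference/SE.

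**All mixed pairs one way (q = 1).** Group 1 variance = 0.16 + 0.10·0.90·0.09 = 0.1681.

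| m₂ | Group 2 variance | Difference (mm) | SE | z | False-positive rate |
|---|---|---|---|---|---|
| 30% | 0.1789 | 0.06 | 0.0833 | 0.72 | 11% |
| 50% | 0.1825 | 0.12 | 0.0837 | 1.43 | 30% |
| 70% | 0.1789 | 0.18 | 0.0833 | 2.16 | 58% |

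**Split 75/25 (q = 0.75).** Group 1 variance = 0.16 + 0.009 − 0.000225 = 0.1688.

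| m₂ | Group 2 variance | Difference (mm) | SE | z | False-positive rate |
|---|---|---|---|---|---|
| 30% | 0.1850 | 0.03 | 0.0841 | 0.36 | 6% |
| 50% | 0.1994 | 0.06 | 0.0858 | 0.70 | 11% |
| 70% | 0.2120 | 0.09 | 0.0873 | 1.03 | 18% |

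**Split 50/50 (q = 0.5).** The difference is 0 and the rate is about 5% throughout. The cost is variance: at m = 50% the SD rises from 0.40 to √(0.16 + 0.045) = 0.453 mm.

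**With the planned test.** Simulating Mann-Whitney on the same inputs gives about 10–11%, 28–29% and 55–56% with all pairs one way, about 6%, 10–11% and 17–19% at 75/25, and about 5% at 50/50. The normal approximation is therefore not driving the result.

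**Smaller shift.** With b = 0.2 mm and all pairs one way, the formula gives about 8%, 16% and 31%.

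**Four groups.** Anatomical location has four levels. Simulating Kruskal-Wallis on four groups of 25 with b = 0.3 mm and all pairs one way gives about 7%, 18% and 39% when two groups have the higher mixed share, and about 7%, 15% and 28% when one does.

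**Equal shares.** With 25% mixed in both groups, all one way, the false-positive rate stays near 5%. Power for a true difference of 0.5 SD falls from about 0.67 to 0.60 if the shift is as large as 1 SD.

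**The case against.** The strongest reply is that no defect has been shown to occur. The wording on film types can mean that both were taken at each visit, or that each patient had one type throughout; in either case same-type pairs would be available. That stands: the document neither shows nor excludes mixed pairs, and a reader who infers that they were used goes beyond the text.

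A reader might also infer that comparisons by jaw region are biased because film choice follows region. Nothing in the document links the two. The Statistical Analysis section names no grouping factor for bone loss, and Outcome Measure Data ties anatomical parameters to survival and complications. The link is an assumption.

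The 58% figure needs a 0.3 mm shift, 70% against 10% mixed, and a single direction, all together. Direction decides whether there is bias at all, so the figure should not be quoted without the range.

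The absence of film type from the clinical parameter list is weak evidence that it was not recorded. The list is introduced as non-exhaustive, and marginal bone loss is not on it either.

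Finally, the concern does not reach the declared primary outcome directly, and setting bone loss to missing for mixed pairs could do harm. Inclusion 5 and exclusion 8 would then remove those patients from the whole study. This is correct, and the fix has to deal with it.

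What survives is that the stated method permits mixed pairs, implant-length calibration does not make the film types interchangeable, and a better rule is available at little cost.

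**Conclusion.** The point holds conditionally and is worth acting on. The endpoint definition lets a film-type difference enter marginal bone loss whenever a patient's two films differ in type. Group comparisons are biased only if mixed pairs run mostly in one direction and their share differs between groups; otherwise the effect is mainly added variance, and with no mixed pairs it is nil. Under the assumed inputs the false-positive rate ranges from the nominal 5% to 58%, depending mainly on direction and imbalance. The document cannot place the study within that range. It does not support saying that the bone-loss results are biased, that location comparisons are confounded by imaging, or that the primary survival and complication results are affected.

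**What to change.** 1. Read the film type at each time point from the films already held, and report the number of mixed pairs. If there are none, one sentence with the counts closes the matter.
2. Compute bone loss only from same-type pairs, using the periapical pair where both kinds of pair exist. Show the results by film type.
3. Keep the all-pairs analysis as a sensitivity analysis.
4. State that a mixed pair does not count as missing bone-loss data under exclusion 8 or as failing inclusion 5, so that these patients stay in the survival and complication analyses.

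The cost is one field per film, a clarification to two eligibility items, and fewer patients in the bone-loss analysis if mixed pairs exist. No new radiographs are needed.

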Analysis Population Information:

Overall Number of Participants Analyzed: 100 participants

Outcome Measure Data Table

Measure Type: Count of Participants

Measure of Dispersion/Precision: Not Applicable

Outcome Measure Data: The effect of prosthetic, anatomical and surgical parameters on implant survival rate and prosthetic complications

Unit of Measure: Implant survival and prosthetic complications rate

Statistical Test of Hypothesis:

P-Value: p<0.05

Method: Chi-Squared

Adverse Event Information: Since this is a retrospective analysis, adverse events were not evaluated.

Certain Agreements:

- **Are all PIs Employees of Sponsor?** Yes: The principal investigator is an employee of the sponsor

Results Point of Contact:

- **Name or Official Title:** [name]. Assistant Professor at Afyonkarahisar Health Sciences University, Department of Prosthodontics.
- **Organization Name:** Afyonkarahisar Health Sciences University
- **[contact]
- **E-mail:** [contact]

Document Upload Information:

- **Document Type:** Study Protocol with Statistical Analysis Plan (SAP)
- **Document Date:** 07.04.2023

This retrospective study included 100 volunteer patients aged between 30 and 77 who presented at the Department of Prosthetic Dentistry at Afyonkarahisar Health Sciences University Faculty of Dentistry for prosthetic treatment and received a single-unit implant-supported crown. The evaluation of the included patients was conducted during their 12-month follow-up control appointments after prosthetic loading. After obtaining oral and written consent from the patients, demographic data, prosthetic complications related to single-unit fixed implant-supported prostheses, and peri-implant bone loss assessed via radiographic controls were recorded and analyzed. During clinical examinations, the compatibility of the prostheses with adjacent teeth and gingiva, the presence of gingival recession, patient complaints about the prosthesis, and any prosthetic complications were assessed and recorded. Statistical analyses were performed retrospectively after evaluating the collected data.

Ethical Approval for the Study

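### The plan aims at the effect of each factor but provides only group summaries and p-values: no between-level effect estimate or confidence interval for complications or bone loss

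*Combined protocol and SAP*

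**What the plan says.** In the Combined protocol and SAP, the outcome measure data table describes the primary outcome data as "The effect of prosthetic, anatomical and surgical parameters on implant survival rate and prosthetic complications". The measure type is a count of participants, with "Measure of Dispersion/Precision: Not Applicable". Under Statistical Test of Hypothesis the entry is "Method: Chi-Squared", at p<0.05.

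The Statistical Analysis section lists summaries first: "Descriptive statistical methods (mean, standard deviation, median, frequency) were employed". It then lists tests: "Quantitative data and intergroup comparisons were evaluated using the Kruskal-Wallis test, with Dunn's test for post hoc analysis", the Mann-Whitney U test for pairwise comparisons, and, for categorical data, "the Fisher-Freeman-Halton Exact Chi-Square test was employed for qualitative data comparisons". It closes by saying that p<0.05 "was considered statistically significant".

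The only mention of a 95% confidence interval is in Volunteer Selection, where it restates the 0.05 significance level of the sample size calculation. It is not a planned output.

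**The concern.** An effect has a size and a precision. The plan names effects of factors as its outcome data, yet the comparisons it specifies end in a p-value. A team that followed it to the letter would hold frequencies, medians and a list of p-values. It would have committed to no contrast, no reference level and no interval.

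The point concerns comparisons between factor levels, not the precision of the overall complication rate. For complications, the missing quantity is a risk difference or ratio. For bone loss it is a difference in millimetres: the Kruskal-Wallis and Mann-Whitney tests give none, and two separate medians carry no interval for their difference.

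If events are few, a non-significant p-value is compatible with anything from no effect to a large one, and without an interval the reader cannot tell which. A significant p-value has the mirror problem: nothing planned says how large the effect is or how well it is known. The Data Collection section lists many factors, several with three to five levels, and records screw loosening, cementation loss and chipping separately. Events per comparison may therefore be fewer than the total suggests.

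**Working it through.** **1. Is an effect estimate planned anywhere?**

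| Place | Planned output | Between-level estimate | Interval |
|---|---|---|---|
| Outcome measure data table | Count of participants | None | Precision marked not applicable |
| Statistical Test of Hypothesis | Chi-squared, p<0.05 | None | None |
| Statistical Analysis, summaries | Mean, SD, median, frequency | None | None |
| Statistical Analysis, tests | Kruskal-Wallis, Dunn, Mann-Whitney, Fisher-Freeman-Halton, p<0.05 | None | None |
| Volunteer Selection | d = 0.5, alpha 0.05, power 0.80 | Design input only | Gloss on alpha |

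There is no planned figure for a factor contrast to reproduce. The d of 0.5 is a standardised mean difference and carries no complication rate. How the 80 patients follow from it is a separate question on which this point does not depend.

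**2. What a p-value alone could conceal**

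Inputs: 100 patients analysed (outcome table); two-sided 0.05 (sidedness is not stated, so assumed); 10 events and a 50:50 factor (both assumed). Take 8/50 against 2/50.

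- Risk ratio: (8/50)/(2/50) = 0.16/0.04 = 4.0.
- SE of log RR: √(1/8 − 1/50 + 1/2 − 1/50) = √0.585 = 0.765.
- 95% CI: exp(1.386 ± 1.96 × 0.765) = exp(−0.113) to exp(2.885) = 0.89 to 17.9.
- Fisher's exact test: p = 0.092.
- Uncorrected Pearson: χ² = 100 × (8×48 − 42×2)² / (50×50×10×90) = 100 × 300² / 2,250,000 = 4.0, p = 0.0455.
- Yates-corrected: p = 0.096.

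The same table falls on either side of 0.05 according to the test. The outcome table says only chi-squared; the Statistical Analysis section names the exact test.

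**3. How far the illustration depends on its assumptions**

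| Events | Split | Table | Risk ratio (95% CI) | Fisher p |
|---|---|---|---|---|
| 5 | 50/50 | 4 v 1 | 4.00 (0.46 to 34.6) | 0.36 |
| 10 | 50/50 | 8 v 2 | 4.00 (0.89 to 17.9) | 0.092 |
| 10 | 20/80 | 5 v 5 | 4.00 (1.28 to 12.5) | 0.026 |
| 10 | 27/73 | 6 v 4 | 4.06 (1.24 to 13.3) | 0.022 |
| 10 | 37/63 | 7 v 3 | 3.97 (1.09 to 14.4) | 0.036 |
| 10 | 70/30 | 9 v 1 | 3.86 (0.51 to 29.1) | 0.27 |
| 15 | 50/50 | 12 v 3 | 4.00 (1.20 to 13.3) | 0.023 |
| 20 | 50/50 | 16 v 4 | 4.00 (1.44 to 11.1) | 0.005 |

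A ratio near 4 gives Fisher p-values from 0.005 to 0.36 over this range. The p-value follows the event count and split as much as the size of the effect. In every row the upper limit is above 11, which a p-value does not show.

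**The case against.** **Frequencies by level already give crude effects.** If the planned summaries are tabulated by factor level, a reader can divide two percentages or subtract two medians. This stands in part: it would be wrong to say that effects could never be recovered. But the plan commits to no contrast or reference level, and supplies no precision.

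**A reader might infer that a fourfold effect will be declared no effect.** The documents do not support that. They give no event count, complication rate or factor split, so 10 events is an assumption. Even at 10 events, a ratio of about 4 is significant by Fisher's test at 20/80, 27/73 and 37/63, and at 50/50 by uncorrected Pearson. Nor does the plan say how p of 0.05 or more will be read; it defines only what counts as significant.

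**A reader might also infer that some 70 to 80% of real two- to threefold differences would be missed.** That holds only for Fisher's test with equal groups or with the higher risk in the smaller group. For a true 5% against 15%, exact power runs from 8% (Fisher, 80 patients at higher risk) to 43% (uncorrected Pearson, 30 at higher risk). Low power is in any case a sample size matter: intervals display imprecision but do not cure it.

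**Intervals depend on method too.** This is true. For 8/50 against 2/50 the simple Wald interval for the risk difference is 0.12 ± 1.96 × √(0.16×0.84/50 + 0.04×0.96/50) = 0.12 ± 0.115, or 0.5 to 23.5 percentage points. It just excludes zero, while the ratio interval includes 1. Both still show great uncertainty, but the interval method should be fixed in advance.

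**The output could swell.** With about 20 variables and at least three complications, two measures for every level would be excessive. This stands, and one measure per comparison is enough.

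**Conclusion.** The point holds. The stated outcome data are effects of factors, but the outcome table and the Statistical Analysis section provide only summaries and tests at p<0.05. Carried out as written, the plan yields no between-level effect estimate and no confidence interval, for complications or for bone loss. This conclusion rests on the text alone.

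Its numerical size is illustrative. It assumes 10 events, an even split and two-sided testing: an observed risk ratio of 4.0 with a 95% CI of 0.9 to 17.9 would appear as p=0.09 or p=0.046, depending on the test. Other splits or event counts can make the same ratio significant. What is supported is that a p-value alone could hide a large effect and can turn on the test chosen. It is not supported that large effects will generally be missed, or that non-significance will be reported as absence of effect. This is an inexpensive improvement that should be made.

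**What to change.** In Statistical Analysis, name a reference level for each factor and add:

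- **Each complication:** one effect measure with a 95% CI, either the risk difference or the risk ratio, chosen in advance with its interval method. Use the exact conditional odds ratio where a cell is zero.
- **Bone loss:** the Hodges-Lehmann difference with its 95% CI.
- **Reporting:** present the estimate and interval as the result, with the p-value beside it, and state which chi-squared or exact test supplies that p-value. Describe non-significant results by their interval, not as absence of effect.

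Change the precision entry in the outcome table to match.

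The cost is SAP wording and more output from data already collected; no further patients are needed. The downside is a longer set of tables, and wide intervals that make the conclusions visibly less definite.

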Retrospective Evaluation of Prosthetic Complications and Peri-implant Bone Resorption in Implant-Supported Single Unit Fixed Restorations

Study Protocol

Date: 07.04.2023

Department of Prosthetic Dentistry

Afyonkarahisar Health Sciences University, Faculty of Dentistry

Pre-assignment Details

Participants included in the study were later excluded from the analysis due to reasons such as missing data in patient records, the presence of data outside the specified time frame, patients initially thought to meet the study criteria being incorrectly coded, or medical records being in an unsuitable format or unreadable.

Arm/Group Information

This study does not include any specific study or control groups. The research focuses on the follow-up of participants with certain characteristics over a specified time period.

Type of Units Assigned

- **Period(s):** This is a retrospective study following a 12-month period.
Period Title: Overall Study
Started: This study was conducted by including patients 12 months after delivery of the implant-supported restoration. The sample was completed when a total of 100 patients were reached.
Completed: The number of participants at the end of the study is 100.

Baseline Characteristics

- **Arm/Group Information:** There were no separate groups in the study. The study included a 12-month follow-up of participants with implant-supported single-unit restorations.
Arm/Group Title: There were no separate groups in the study.
- **Baseline Analysis Population Information**
Overall Number of Baseline Participants: 100 participants
- **Baseline Measure Information**
Baseline Measure Title
Age: Age, Continuous
Sex/Gender: Female, Male
- **Measure Type:** Count of Participants

- **Measure of Dispersion:** Not Applicable
- **Baseline Measure Data: Not Available.** The study does not have any baseline data, because the data in the study only includes data from participants at the end of the 12-month follow-up.
- **Unit of Measure:** Not Available

Outcome Measures:

- **Outcome Measure Information:** Implant survival and prosthetic complication rate
 - Outcome Measure Type:** Primary
 - Outcome Measure Title:** Implant survival and prosthetic complication rate
 - Outcome Measure Time Frame:** 12 months after delivery of implant-supported restoration
 - Arm/Group Information:** There were no separate groups in the study. The study included a 12-month follow-up of participants with implant-supported single-unit restorations.

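### About 10 parameters are tested against survival and complications at an unadjusted p<0.05, with no primary comparison and no exploratory label, so chance findings would be reported as significant effects

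*Combined protocol and SAP*

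**What the plan says.** Under Outcome Measures the primary outcome is "Implant survival and prosthetic complication rate", a single title that covers two outcomes. The Outcome Measure Data entry describes it as "The effect of prosthetic, anatomical and surgical parameters on implant survival rate and prosthetic complications". The Statistical Test of Hypothesis entry gives "P-Value: p<0.05" and "Method: Chi-Squared". Association tests are therefore attached to the primary outcome.

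On the cohort itself the document says: "There were no separate groups in the study". No default contrast follows from the design.

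The Statistical Analysis section adds that "the Fisher-Freeman-Halton Exact Chi-Square test was employed for qualitative data comparisons" and ends with the general rule: "A significance level of $p<0.05$ was considered statistically significant". Its only step aimed at multiple comparisons is Dunn's test. That step follows a Kruskal-Wallis test on quantitative data and does not reach the categorical survival and complication tests.

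The document does not state the number of tests, a primary parameter or comparison, an adjustment across parameters or outcomes, or that the associations are exploratory.

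**The concern.** Under the stated rule, any single p-value just below 0.05 is reported as a significant effect of that parameter, and the reader cannot see how many tests it was picked from.

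A hypothetical example: a complication occurs in 6 of 30 patients with one level of a factor and in 3 of 70 with the other. Fisher's exact test gives p = 0.020. The odds ratio is (6 × 67)/(24 × 3) = 5.6, with a 95% interval of 1.3 to 24. The plan would call this significant. With 20 tests the first Holm threshold is 0.05/20 = 0.0025, and the result falls well short of it.

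What is at stake is a claim that, say, abutment type or material affects complications when the result is one chance finding among many. The 12-month rates do not depend on this.

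**Working it through.** **Plan's own figure.** None exists to reproduce: the document states a per-test threshold of 0.05 and no error rate for the set of tests.

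**Inputs from the document**
- Patients analysed: 100.
- Threshold: 0.05 for every test.
- Test for categorical data: Fisher-Freeman-Halton exact (Statistical Analysis) or chi-squared (Statistical Test of Hypothesis).
- Parameters (Data Collection, B. Clinical Parameters): items 6 to 15 are ten surgical, anatomical and prosthetic parameters. Implant length has one level only and cannot be tested, which leaves nine; attached gingiva (item 5) makes ten.
- Levels: two for attached gingiva, immediate placement, implant type and occlusal table; three for extraction reason, diameter, abutment and material; four for location; five for opposing arch.
- Outcomes: one to four, depending on the reading. Two is survival and any complication. Three is screw loosening, cementation loss and chipping separately. Four adds ICOI status. One is a combined complication alone.

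**Assumptions (not in the document)**
- No association is real.
- Each outcome is binary (ICOI status collapsed to two levels) with 5 to 20 events.
- Factor splits are balanced, moderate (such as 70/30 or 50/30/20) or skewed (such as 85/15 or 75/15/10).
- Tests are independent; this is relaxed below.

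**Method.** For a factor with group sizes n_j and m events, each table has probability ∏C(n_j, x_j)/C(100, m). Enumerating all tables gives the true size s_i of the exact test at p<0.05, which with few events is usually below 0.05. For K outcomes:
- expected chance findings = K × Σ s_i
- chance of at least one = 1 − [∏(1 − s_i)]^K

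The lowest case is balanced splits with 5 events: Σ s_i = 0.213 and ∏(1 − s_i) = 0.804. The highest is skewed splits with 15 events: Σ s_i = 0.485 and ∏(1 − s_i) = 0.608. For four outcomes, 1 − 0.804⁴ = 58.2% and 1 − 0.608⁴ = 86.3%.

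| Outcomes | Tests | Expected chance findings | At least one |
|---|---|---|---|
| 1 | 10 | 0.21–0.48 | 19.6–39.2% |
| 2 | 20 | 0.43–0.97 | 35.3–63.0% |
| 3 | 30 | 0.64–1.45 | 48.0–77.5% |
| 4 | 40 | 0.85–1.94 | 58.2–86.3% |

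For comparison, a true size of exactly 0.05 would give 1 − 0.95²⁰ = 64% and 1 − 0.95⁴⁰ = 87%.

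**Sensitivity**
- *Correlated tests* (simulation with 5, 10 and 20 events, correlation 0.3 and 0.5 among factors and among outcomes, 3,000 runs per setting): 32–57% for 20 tests, 43–71% for 30, 53–81% for 40. With Holm, at most 4.2%.
- *Eight parameters* (without attached gingiva and extraction reason): 29–55% for two outcomes, 40–70% for three, 50–80% for four.
- *Two or three events, ten parameters*: 0–47% for two outcomes, 0–61% for three, 0–72% for four. The zero is for 2 events with balanced factors.
- *Pearson chi-squared instead of the exact test*: 33–76% for 20 tests, 45–88% for 30, 55–94% for 40.

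**The case against.** The strongest point is about survival. The Exclusion Criteria remove "Patients who lost implants before the 12-month follow-up", so survival in the literal sense can hardly vary, and the two-outcome reading may shrink to one outcome. The figure is then 20–39%, or 16–33% with eight parameters. The four-group ICOI scale can still vary, but the document does not show that 5 to 20 patients would fall on one side of any cut. This stands as a reason to quote the one-outcome figure beside the others.

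The event floor of 5 is also an assumption. At 3 events with balanced factors the risk is 7% for two outcomes and 13% for four. At 2 to 3 events with uneven factors it is again 36–47% for two outcomes. This widens the range but does not remove the problem.

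Some pairs may not be null by definition, such as chipping against monolithic materials or cementation loss against screw-retained abutments. That affects few of the 30 to 40 tests. Where associations are real, fewer tests are null and the expected counts fall.

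Finally, this is a single-cohort retrospective study whose primary measure is a rate, and whether such association tests need formal adjustment is debated. That is a fair argument for an exploratory label without adjustment. It does not support the present text, which has neither and calls every p<0.05 significant.

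One omission runs the other way. Mesial and distal bone loss, age, sex, education and tooth brushing are not in the count; testing them would raise it.

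**Conclusion.** The concern holds. The plan attaches a set of unadjusted association tests to its primary outcome and gives the reader no means of weighing an isolated significant result. With ten parameters, 5 to 20 events per outcome, exact independent tests and no real association, at least one chance finding is 35–63% likely with two outcomes and 58–86% likely with four. The event counts and factor splits are assumptions, and very sparse outcomes could bring the risk close to zero. The direction does not depend on the choice of exact or Pearson test, on eight or ten parameters, or on moderate correlation. The change is worth making because it is cheap, though confidence in the exact size is only medium.

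**What to change.** In Statistical Analysis:
1. State the outcomes and the number of parameter-by-outcome tests.
2. Report the complication rate and the ICOI distribution with 95% intervals as the primary result. Note that survival describes only implants still present at 12 months. For scale, 5/100 has an exact interval of 1.6–11.3%, and 20/100 has 12.7–29.2%.
3. Label all parameter associations exploratory. Give effect estimates, 95% intervals and unadjusted p-values, without calling an isolated p<0.05 a significant effect.
4. If an association is to be claimed as significant, give Holm-adjusted p-values across the declared family. The document is written in the past tense; if the data have already been analysed, disclose that the family is post hoc.

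**Cost.** Revised text, plus estimates and intervals from existing data. Some nominally significant results lose that label. Holm has little reach when events are sparse: for a 50/50 factor with m events the smallest attainable p is 2 × C(50, m)/C(100, m), which is 0.0058 at 8 events, 0.0026 at 9 and 0.0012 at 10. The first Holm thresholds are 0.0025, 0.0017 and 0.00125 for 20, 30 and 40 tests, so such a factor cannot pass the first step with fewer than 10 events. That is a further reason to make the exploratory label the main remedy.
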